#### \*Population

## For CAB+RPV LA:

#### Inclusion criteria:

- People with HIV
- $\geq$ 18 years old
- Treatment experienced
- Active in care in OPERA defined as having a clinical encounter in the 24 months prior to 31DEC2023, 31DEC2024, 31DEC2025

ViiV Healthcare Protocol Final 216990 – Amendment 3

• Received at least one CAB+RPV LA injection between 21JAN2021 and 31DEC2023, 31DEC2024, 31DEC2025

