#### For Guidelines Recommended Oral ART:

#### Inclusion criteria:

- People with HIV
- ≥18 years old
- Treatment experienced
- Active in care in OPERA defined as having a clinical encounter in the 24 months prior to 31DEC2024, 31DEC2025
- Received a prescription for a new oral ART regimen (recommended by the DHHS guidelines as first-line therapy at the time of analysis)
- Virologically suppressed (VL <50 copies/mL) at start of new oral ART regimen

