#### **Secondary Objectives:**

- 1. Sub-group analyses by viral load (VL <50, ≥50copies/mL) at initiation, BMI (<30 and ≥30 kg/m²) at initiation and age (18-50, 50-64, ≥65 years) at initiation to assess characteristics, adherence, persistence, discontinuation and virologic effectiveness
- 2. To estimate the frequency of documented injection site reactions and hypersensitivity reactions among PWH receiving CAB+RPV LA injections at Year 3, Year 4, and Year 5 of availability
- 3. To compare baseline characteristics and treatment outcomes (persistence/discontinuation, adherence, maintaining virologic suppression, confirmed virologic failure) between oral ART and CAB+RPV LA use in PWH at Year 4 and Year 5 of availability
- 4. To describe baseline characteristics and treatment outcomes (persistence/discontinuation, adherence, virologic effectiveness) among PWH receiving CAB+RPV LA injections at Year 4 and Year 5, in subgroups of interest
  - a. Race/ethnicity (Non-Hispanic Black, Hispanic, Non-Hispanic White)
  - b. Sex/race (Non-Hispanic Black men, Hispanic men, Black women)
- 5. Among individuals with confirmed virologic failure (CVF): to describe HIV resistance and proviral testing at the time of CVF, as well as history of resistance and proviral DNA testing prior to CVF at Year 4 and Year 5 of availability

ViiV Healthcare Protocol Final 216990 – Amendment 2

- 6. Among individuals with confirmed virologic failure (CVF): to describe the ART regimens after CVF in OPERA at Year 4 and Year 5 of availability
  - a. To describe the baseline characteristics (demographic, clinical, treatment patterns) of ART regimen after CVF
  - b. To describe virologic response (suppression, non-response, confirmed virologic failure) to ART regimen after CVF

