#### **Inclusion criteria:**

- People with HIV
- ≥18 years old
- Treatment experienced
- Active in care in OPERA defined as having a clinical encounter in the 24 months prior to 31DEC2023, 31DEC2024, 31DEC2025
- Received a new ART regimen of interest between 21JAN2021 and 31DEC2023, 31DEC2024, 31DEC2025
  - At least one CAB+RPV LA injection or
  - A prescription for a new oral ART regimen recommended by the DHHS guidelines

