#### 6.3.3. Confounders and effect modifiers

#### 6.3.3.1. Confounders

The following baseline characteristics will be evaluated as potential confounders:

- Demographic characteristics at index
  - Age (years, as well as categorized as 18-50, 50-64, 65+)
  - Sex (male, female)
  - Race (African American/Black, Asian, White, other race, unknown)
  - Ethnicity (Hispanic, non-Hispanic)
  - Marital status (Single, married/domestic partner, widowed, separated/divorced, unknown)
  - Geographic region (Northeast, Midwest, South, West, US Territories)
  - Risk of HIV transmission (MSM, PWID, Heterosexual, Vertical, Other)
  - Payer type (Medicaid, Medicare, Commercial insurance, AIDS Drug Assistance Programs (ADAP)/Ryan White, Cash)
- Clinical characteristics at index
  - Years since HIV diagnosis
  - Years since ART initiation
  - AIDS diagnosis at baseline

- Years since first OPERA visit
- Veterans Aging Cohort Study (VACS) Mortality Index score
- Weight (kg)
- $\circ \quad BMI (<30 \text{ vs.} \ge 30 \text{ kg/m}^2)$
- Co-infections
  - Hepatitis B co-infection
  - Hepatitis C co-infection
  - Syphilis infection (ever)
- o Comorbidities
  - Autoimmune disease
  - Cardiovascular disease
  - Invasive cancer
  - Endocrine disorder
  - Mental health disorder
  - Liver disease
  - Bone disorder
  - Peripheral neuropathy
  - Renal disease
  - Hypertension
  - Substance abuse
  - Any of the above
- Concomitant Medications
  - Anticonvulsants
    - Carbamazepine
    - Oxcarbazepine
    - Phenobarbital
    - Phenytoin
  - Antimycobacterials
    - Rifampin
    - Rifapentine
    - Rifabutin
  - Glucocorticoids
    - Dexamethasone
  - Macrolide or ketolide antibiotics
    - Azithromycin
    - Clarithromycin
    - Erythromycin
  - Narcotic analgesic
    - Methadone
- ART regimens prior to CAB+RPV LA
  - Number of core agents experienced
  - o Number of ARV classes experienced
  - Duration of last ARV regimen
  - o Prior core agent class
- Baseline virologic characteristics
  - o HIV viral load
    - Test result available (yes/no)
    - Continuous (copies/mL and log10 copies/mL)

- Categorical
  - o <50 copies/mL
  - $\circ$   $\geq$ 50 to  $\leq$ 200 copies/mL
  - $\circ \geq 200 \text{ to } < 1,000 \text{ copies/mL}$
  - $\circ \ge 1,000 \text{ to} < 10,000 \text{ copies/mL}$
  - $\circ \ge 10,000 \text{ to } < 100,000 \text{ copies/mL}$
  - $0 \ge 100,000 \text{ copies/mL}$
  - Missing
- Baseline immunologic characteristics
  - o CD4 cell count

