## 6.5. \*Study size

Over two years (21JAN2021 and 28FEB2023), there were 1,843 individuals who were 18 years of age or older with HIV-1 in OPERA who were active in care and had received their first CAB+RPV injection. Of these, 1,578 had viral loads <50 copies/mL at first injection, and 229 had viral loads ≥50 copies/mL (36 had no viral load data available at first injection). Study size is expected to grow for Year 3, Year 4, and Year 5 making these calculations underestimates.

Confidence intervals, constructed using the asymptotic (Wald) method based on a normal approximation, are presented in Table 1, and are designed to give estimates of precision for a variety of sample sizes and event probabilities.

The example sample sizes in Table 1 reflect the overall sample size as well as the strata based on viral load at first CAB+RPV LA injection.

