# 6.7. \*Data analysis

# 6.7.1. Primary Analysis

## 6.7.1.1. Main Analytical approach

Baseline characteristics and outcomes will be described using counts and absolute and relative frequencies for categorical variables and medians with interquartile ranges (IQR) for continuous variables. For outcomes assessed at any point during follow-up, incidence rates will be estimated using unadjusted Poisson regression, accounting for person-time since index (i.e., first CAB+RPV LA injection).

Analyses will be stratified by viral load (<50 copies/mL vs. ≥50 copies/mL), BMI (<30 kg/m² vs. ≥30 kg/m²), age (18-50, 50-64, ≥65 years), race/ethnicity (non-Hispanic Black, Hispanic, non-Hispanic White), and sex/race (non-Hispanic Black men, Hispanic men, Black women) strata at first CAB+RPV LA injections as sample size allows to assess characteristics, adherence, persistence, discontinuation and virologic effectiveness. Other demographic and clinical variables may also be considered for stratification, if relevant.

Factors including age, sex, race, geographic region, BMI, IDU, CD4 count, any comorbidities associated with confirmed virologic failure will be assessed using multiple logistic regression.

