# 6.7.2. Secondary analysis/Exploratory analysis

Not applicable

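### Secondary objective 3 compares oral ART with CAB+RPV LA, but the viral-load entry rules for the two groups are inconsistent and no stated analysis of the comparison uses the listed confounders

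*Protocol*

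**What the plan says.** - **Objective.** Secondary objective 3 in Section 5, due at Years 4 and 5, is "To compare baseline characteristics and treatment outcomes (persistence/discontinuation, adherence, maintaining virologic suppression, confirmed virologic failure) between oral ART and CAB+RPV LA use in PWH".
- **Injectable entry, Synopsis.** The exposure criterion is "Received at least one CAB+RPV LA injection between 21JAN2021 and 31DEC2023, 31DEC2024, 31DEC2025". No viral-load criterion appears.
- **Oral entry, Synopsis.** The list adds "Virologically suppressed (VL <50 copies/mL) at start of new oral ART regimen".
- **Oral entry, Section 6.2.** The corresponding line is "A prescription for a new oral ART regimen recommended by the DHHS guidelines", with no viral-load condition. The injectable line has none either.
- **Index date.** Section 6.2 ties it to the first regimen of interest, so it covers both regimens.
- **Rates, Section 6.7.1.1.** For outcomes assessed at any time, "incidence rates will be estimated using unadjusted Poisson regression", with person-time counted from the first CAB+RPV LA injection.
- **Other analysis text.** The same section has one multivariable model, a logistic regression for factors associated with confirmed virologic failure. Section 6.7.1.2 plans no sensitivity analyses. Section 6.7.2, on secondary and exploratory analysis, reads "Not applicable".
- **Confounders, Section 6.3.3.1.** "The following baseline characteristics will be evaluated as potential confounders", followed by a long list that includes viral load, payer, prior regimens and comorbidities.

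**The concern.** A comparison of outcomes between two regimens needs one definition of who is compared and a stated way of handling differences between the groups at the start. The oral cohort was added in Amendment 3, and the analysis text does not appear to have followed it.

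Two things are at stake. First, under the Synopsis one side is wholly suppressed at the start and the other need not be; under Section 6.2 neither need be. Two analysts could build different cohorts from the same protocol. Second, people chosen for injections may differ from people switching oral regimens in payer, comorbidity, treatment history and calendar time. If only the stated analyses are run, the result is an unadjusted contrast. Section 10 names regulators, health plans and clinicians as the audience, and they could read it as a regimen effect.

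**Working it through.** **1. Entry rules side by side**

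| | CAB+RPV LA | Oral ART |
|---|---|---|
| Synopsis | no viral-load rule | below 50 copies/mL at start |
| Section 6.2 | no viral-load rule | no viral-load rule |

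The two places disagree on the oral cohort. Neither restricts the injectable cohort.

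**2. How many injectable starters are affected**

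Section 6.5 (21 January 2021 to 28 February 2023) reports that "1,578 had viral loads <50 copies/mL at first injection, and 229 had viral loads" of 50 or more; 36 had no result.
- Total: 1,578 + 229 + 36 = 1,843, as stated.
- Viremic: 229 / 1,843 = 12.4%. Among those with a known viral load, 229 / 1,807 = 12.7%.
- No result: 36 / 1,843 = 2.0%.
- Not shown to be below 50: (229 + 36) / 1,843 = 265 / 1,843 = 14.4%.

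**3. Which outcomes the mismatch reaches (Sections 6.3.2.3 to 6.3.2.6)**
- Maintaining suppression is defined only for people below 50 copies/mL at baseline, so it is unaffected.
- Confirmed virologic failure has separate definitions for suppressed and viremic starters, and the viremic one requires prior suppression. No pooled definition exists.
- Persistence, discontinuation and adherence carry no baseline viral-load condition. The mismatch falls mainly here.

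**4. What it could do to those outcomes**

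Suppose all injectable starters with a known viral load were compared with a fully suppressed oral cohort, and regimen made no difference. For an outcome whose risk in viremic starters is R times that in suppressed starters, the apparent ratio is 1 + f(R − 1), with f = 229 / 1,807 = 0.127. For assumed R of 1, 2 and 3 this gives 1.00, 1.13 and 1.25. The document gives no R for persistence, discontinuation or adherence, so these values only show how the formula behaves.

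**5. Stated analyses set against objective 3**
- Unadjusted Poisson rates: no covariates, and the time origin fits injectable users only, although the index date in Section 6.2 covers either regimen.
- Logistic model for failure: it serves primary objective 4, which concerns CAB+RPV LA users. The named factors are age, sex, race, region, BMI, injection drug use, CD4 count and comorbidities. Regimen is absent.
- Viral-load strata (Sections 6.3.3.2 and 6.7.1.1): set at the first injection, with no statement that objective 3 uses the suppressed stratum.
- Section 6.7.2, where a secondary comparison would be expected, states that nothing applies.

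No item links the Section 6.3.3.1 list to the oral-versus-injectable contrast.

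**6. Precision cost of restricting the injectable side**

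Table 1 uses Wald intervals: width = 2 × 1.96 × √(p(1 − p)/n). All 44 rows reproduce within rounding. The maxima at p = 0.5 are:
- n = 1,843: 0.0457 (stated 0.05)
- n = 1,578: 0.0493 (stated 0.05)
- n = 136: 0.1681 (stated 0.17)
- n = 93: 0.2032 (stated 0.20)

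Restriction keeps 1,578 / 1,843 = 85.6% of starters, and the maximum width moves from 0.046 to 0.049. These widths describe single proportions; the protocol gives no precision for the comparison itself.

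**The case against.** The strongest reply is that the protocol already points to a like-for-like contrast. Objective 3 names maintaining suppression and omits the outcomes specific to viremic starters (achieving suppression, non-response). The planned strata yield a suppressed injectable group, and with 1,578 such people the sample-size proviso is no obstacle. The unadjusted Poisson sentence refers to the first injection, so it may describe only the injectable cohort and not prescribe the comparison. Section 6.9.1 calls the analyses descriptive. Model details may sit in a statistical analysis plan that is not shown.

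Much of this stands. A reader might infer that all injectable users are to be pooled against suppressed oral users, so that the comparison is confounded by design. The document never says so, and the planned stratification tells against it. A reader might also work out an inflated failure ratio: with f = 0.127 and an assumed viremic-to-suppressed risk ratio of 3 to 10, the formula above gives 1.25 to 2.14. That figure depends on assumed risks and on a pooled failure outcome that Section 6.3.2.6 does not define. Since viremic starters must first suppress before they can count as failures, even its direction is uncertain.

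What the reply does not remove is the disagreement between Synopsis and Section 6.2, the lack of any statement that objective 3 uses the suppressed stratum, and the entry in Section 6.7.2. Stratifying by viral load also leaves payer, comorbidity, prior regimen and calendar time untouched. A later analysis plan can choose the model, but it should not have to decide who is in the cohort or override a protocol statement that no secondary analysis applies.

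**Conclusion.** The point holds in limited form: the population for objective 3 is inconsistently defined, and no stated analysis of that comparison uses the confounders the protocol lists. It concerns one of six secondary objectives; the primary objectives are unaffected.

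In the data to 28 February 2023, 12.4% of injectable starters were viremic and a further 2.0% had no viral load. The shares at Years 4 and 5, when the comparison is run, may differ. The viral-load mismatch bears mainly on persistence/discontinuation and adherence. Neither its effect nor that of the remaining confounding can be derived from the document.

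**What to change.** 1. Reconcile the Synopsis population criteria with Section 6.2.
2. State in both places that objective 3 uses starters below 50 copies/mL at index in both cohorts. Report viremic injectable starters separately, and say that those without a viral load are outside this comparison.
3. In Section 6.7.1.1, define person-time from the index date of either regimen.
4. Replace the entry in Section 6.7.2 with a covariate-adjusted or propensity-weighted comparison using the Section 6.3.3.1 confounders plus calendar time of index. Keep unadjusted rates as descriptive. The exact model or weighting scheme can be left to the statistical analysis plan.

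**Cost.** Mostly wording, plus modest analysis work on baseline variables the protocol already lists and the index date. On the Section 6.5 counts, 265 of 1,843 injectable starters leave this one comparison (229 viremic, 36 without a result), and the maximum 95% interval width for a proportion in that group goes from 0.046 to 0.049. Adjustment or weighting may widen intervals somewhat further.

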#### Exclusion criteria:

- Received oral ART regimen as part of a clinical trial
- Treatment naïve

#### \*Variables

#### Outcomes:

- Persistence
- Discontinuation
- Adherence
- Virologic effectiveness
- Resistance/Proviral DNA testing

#### Potential confounders to be evaluated:

 Baseline: age, gender, race, ethnicity, region, marital status, risk of HIV transmission, payer type, CD4 cell count, viral load, prior regimen, years since HIV diagnosis and ART initiation, weight, BMI, co-infections, comorbidities, concomitant medications

#### \*Data sources

The OPERA cohort is a multi-site observational database built from the complete patient health records managed in EHR systems from more than 400 participating healthcare providers at 142 separate locations throughout the US. OPERA-participating physicians and ancillary healthcare providers have documented the care of over 1 million patients in their EHRs, including over 150,000 PWH of which approximately 20% are women, representing 13% of all the PWLH linked to care in the U.S.

#### \*Study size

Over two years (21JAN2021 and 28FEB2023), there were 1,843 individuals who were 18 years of age or older with HIV-1 in OPERA who were active in care and had received their first CAB+RPV injection. Of these, 1,578 had viral loads <50 copies/mL at first injection and 229 had viral loads ≥50 copies/mL (36 had no viral load data available at first injection). Study size is expected to increase over the course of this study.

#### \*Data analysis

Baseline characteristics and outcomes will be described using counts and relative frequencies for categorical variables and medians with interquartile ranges (IQR) for continuous variables. For outcomes assessed at any point during follow-up, incidence rates will be estimated using unadjusted Poisson regression, accounting for person-time since index (i.e., first CAB+RPV LA injection). Analyses will be stratified by viral load (<50 copies/mL vs. ≥50 copies/mL), BMI (<30 kg/m2 vs. ≥30 kg/m2), age (18-50, 50-64, ≥65 years), race/ethnicity (non-Hispanic Black, Hispanic, non-Hispanic White), and sex/race (non-Hispanic Black men, Hispanic men, Black women) strata at initiation of CAB+RPV regimen. Factors associated with confirmed virologic failure will be assessed using multiple logistic regression.

# 2. \*AMENDMENTS AND UPDATES

Amendme nt or update no	Date	Section of study protocol	Amendmen t or update	Reason
1	17 May 2024	Study objectives and study population	Amendment 1	Extending the study for additional 3 years Study population:  • Including PWH 13 years and older  • Excluding treatment naïve individuals Primary objective:  • Factors associated with confirmed virologic failure is listed as a separate primary objective  Secondary objective:  • Sub-group analyses are listed as a secondary objective  Oral lead-in and oral bridging will not be assessed
2	05 Sep 2024	Study objectives, study population and outcome definitions	Amendment 2	
 
Secondary objective:         
 
Updated sub-group analyses by viral load stratification - VL <50, ≥50 copies/mL at initiation
 
Study population:

ViiV Healthcar	e	_		Protocol Final 216990 – Amendment 3
ViiV Healthcar	e e			Protocol Final 216990 – Amendment 3  CAB+RPV LA regimen  Added virologic non-response after 6 and 12 months following initiation of CAB+RPV LA regimen  Added confirmed virologic failure definition and included time points during 6 months, 6, 12, 24, 36, 48 and 60 months following initiation of CAB+RPV LA regimen  2. For suppressed at initiation (VL <50 copies/mL):  Included additional time points 36, 48 and 60 months following initiation of CAB+RPV LA regimen  7. For suppressed at initiation (VL <50 copies/mL):  Included additional time points 36, 48 and following initiation of CAB+RPV LA regimen for maintaining
				virologic suppression and CVF definitions
3	23 April 2025	Study objectives and study population	Amendment 3	Adding the following secondary objectives:      1. To compare baseline characteristics and treatment outcomes (persistence/discontinuati on, adherence, maintaining virologic suppression, confirmed virologic failure) between oral ART and CAB+RPV LA use  2. To describe baseline characteristics and treatment outcomes

ViiV Healthcare		Protocol Final
	246000	Amandment 2

				216990 – Amendment 3
				on, adherence, virologic
				effectiveness) among
				PWH on CAB+RPV LA
				in new subgroups of
				interest - Race/ethnicity
				(Non-Hispanic Black,
				Hispanic, Non-Hispanic
				White) and Sex/race
				(Non-Hispanic Black
				men, Hispanic men,
				Black women)
				3. Among individuals with confirmed virologic
				failure (CVF): to describe
				HIV resistance and
				proviral DNA testing at
				failure and history of
				resistance and proviral
				DNA testing
				4. Among individuals with
				confirmed virologic
				failure (CVF): to describe
				clinical characteristics
				and virologic outcomes
				on ART regimen after
				CVF
				Study population: Including PWH
				prescribed with new oral
				guidelines-recommended ART
				regimens
< <n>>></n>	< <date>></date>	< <text>>></text>	< <text>>></text>	< <text>></text>

# 3. \*MILESTONES

Milestone	Planned date
Draft protocol	December 2023
Final protocol	February 2024
Analysis Start Date	April 2024
Yr 3 Preliminary Tables	May 2024
Yr 3 Final Tables	August 2024
Yr 4 Preliminary Tables	May 2025

ViiV Healthcare Protocol Final 216990 – Amendment 3

		,
Yr 4 Final Tables	August 2025	
Yr 5 Preliminary Tables	July 2026	
Yr 5 Final report of study results	October 2026	

#### 4. \*RATIONALE AND BACKGROUND

Antiretroviral therapy (ART) has transformed human immunodeficiency virus (HIV) infection from a fatal illness to a chronic disease.[1] The advancements in antiretroviral therapy (ART) over the past three decades have produced a marked reduction in both morbidity and mortality associated with HIV infection. Since then, the introduction of single-tablet regimens (STR) and once-daily dosing has been associated with increased adherence and improved clinical outcomes in HIV and other illnesses. To further improve HIV treatment options, recent clinical development has been focused on long-acting formulations; formulations that may be dosed once-weekly, once-monthly, and once-bi-monthly. Various routes of delivery for these long-acting formulations are currently being explored, including oral delivery, intravenous infusion, intra-muscular injection, subcutaneous injection, and implantable/removable device delivery.[2-6]

Cabenuva®, a 2-drug co-packaged product of Cabotegravir, a human immunodeficiency virus type-1 (HIV-1) integrase strand transfer inhibitor (INSTI), and Rilpivirine, an HIV-1 non-nucleoside reverse transcriptase inhibitor (NNRTI), is indicated as a complete regimen for the treatment of HIV-1 infection in adults to replace the current antiretroviral regimen in those who are virologically suppressed (HIV-1 RNA less than 50 copies per mL) on a stable antiretroviral regimen with no history of treatment failure and with no known or suspected resistance to either Cabotegravir or Rilpivirine.

The novel long-acting ART therapy delivered through intramuscular injection – CAB+RPV LA – has been shown to be non-inferior to daily oral therapy. Prior to starting the regimen, the healthcare provider (HCP) should carefully select people with HIV (PWH) who agree to the required injection schedule and counsel individuals about the importance of adherence to scheduled dosing visits to help maintain viral suppression and reduce the risk of viral rebound and potential development of resistance associated with missed doses.

CAB, in combination with RPV, has a prolonged PK which presents patients with the opportunity to take their HIV treatment once monthly or once every two months instead of daily; potentially allowing for much improved adherence. While clinical studies have established the efficacy, safety and tolerability of Cabenuva®, this study will assess the utilization patterns, adherence and effectiveness of the regimen in the real-world clinical setting. Understanding patient characteristics and clinical outcomes of this regimen in a heterogeneous population is of great importance to providing optimal care for PWH.

